Secondary Outcome(s)	
 1. Evaluate effect of third dose COVID-19 vaccine booster (BNT162b2 versus mRNA-1273) on Anti-Spike and SARS-CoV-2 viral neutralization at 1 month following booster dose. 2. Anti-Spike and Anti-RBD response at study enrolment, 3 months, 6 months and 12 months following booster dose. 3. Flow cytometry on PBMC, single-cell RNA sequencing and ELISPOT prior to, 1 month, and 6 months following booster dose to evaluate SARS-CoV-2 specific B and T-Cell response. 4. Evaluate adverse effects related to third dose of vaccine through a questionnaire 48 hours -14 days, and 30 days following third vaccine dose. 5. Differences in COVID-19 infections, symptomatic COVID-19 infections, hospitalization, and death between study groups.
Statistical Analysis	
Intention to treat analysis for the primary outcome with two Chi-Squared test or Fisher's exact test for the primary outcome. Non-parametric testing for differences in antibody level between study groups. Mixed effects models will be used for comparison of longitudinal antibody levels.

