2.2 Clinical Data to Date

Given this significant knowledge gap, we conducted the SMASH-COVID-19 Study (Serial Measurement of Quantitative COVID-19 Antibodies in Hemodialysis and Peritoneal Dialysis Patients following COVID-19 Vaccination) in hemodialysis patients at Sunnybrook Health Sciences Centre to determine their humoral response to vaccination. In this prospective observational study, humoral response was compared in 66 hemodialysis patients sampled 28 days after receipt of one dose of vaccine to 76 patients who received two doses of vaccine sampled 14 days after the second dose. Among those receiving one dose, 6% had anti-RBD response above the median level of convalescent serum versus 41% who received two doses after 28 days. Given this finding, it was concluded that hemodialysis patients exhibit a poor humoral response to a single dose of BNT162b2 vaccine and the second dose should not be

delayed.¹⁴ Furthermore, longitudinal follow-up at 13 weeks of our cohort of vaccinated hemodialysis patients has demonstrated that some individuals do not seroconvert and a significant proportion of individuals who attained convalescent serum levels of COVID-19 antibodies (anti-Spike and anti-RBD) exhibit declining antibody levels by 13 weeks as shown in Figure 1, which has not been observed in the general population. This single centre pilot study has led to a larger multi-centre study in Ontario and British Columbia entitled “Determining the Safety and Efficacy of COVID-19 Vaccination in the Chronic Kidney Disease Population” (CTO Protocol Number 3604) which is continuing to recruit patients with chronic kidney disease stage 3b-5. This study will follow serologic response to COVID-19 vaccination in patients with advanced chronic kidney disease including those on dialysis for a one year period to better understand the duration of humoral immunity in this patient population.

[figure not shown]

Figure 1: SARS-CoV-2 IgG Anti-RBD Response Following BNT162b2 Vaccine in Hemodialysis Patients up to 13 weeks following second dose of vaccine.

Patients have been divided into 5 clusters by k-clustering based on trajectory of anti-RBD response over time. Cluster 1 (orange) generally obtained robust response following vaccination

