and maintains serologic response 13 weeks. Clusters 2 (yellow) had an Anti-RBD response but gradually exhibits declining titers, and 3 (green) was characterized by the presence of anti-RBD antibodies at the time of the second dose, either due to previous infection, response to the first dose, or both; in this group, most individuals retained antibodies at 13 weeks, similar to the Cluster 1 (orange), but some of the participants had more rapid decline in antibody levels. Cluster 4 (blue) generally did not achieve seroconversion following vaccination. Cluster 5 (purple) attained seroconversion but did not have an initial robust response defined as reaching convalescent serum levels and generally exhibits declining antibody levels over time. Antibody levels are reported as relative ratios to synthetic standards. Dots represent individual serum samples collected at the indicated times, and the samples from the same patients are connected by lines. Seroconversion threshold represents a positive test and is 0.186 and is indicated by the dashed line. The median level of antigen in convalescent serum taken 21-115 days post-symptom onset is considered a robust antibody response and is 1.25 for anti-RBD.

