Prior to receiving a third vaccine dose, quantitative SARS-CoV-2 IgG antibody levels against the full-length spike protein S1 domain, and Receptor Binding Domain (RBD) to assess humoral response will be measured and Anti-SARS-CoV-2 nucleocapsid protein to measure evidence of prior COVID-19 infection. In addition, we will isolate peripheral blood mononuclear cells in a subset to evaluate cellular immune response, however this will only be performed at University Health Network and Sunnybrook Health Sciences Centre as only these centres have the capacity for processing these samples. A neutralization antibody assay developed by the [name] lab will also be used to assess for viral neutralization prior to booster dose at 1 month (30 days) post third dose of vaccine.

[figure not shown]

Figure 2: Four study groups in the BOOST KIDNEY study. Study participants will be randomized 1:1 after stratification by initial vaccine type.

Following the intervention, SARS-CoV-2 antibodies will be measured 1 month, 3 months, 6 months and 12 months post booster vaccination. Neutralizing antibodies will be measured at baseline and 1 month post third dose of booster vaccine. Cellular immunity in a subset will be evaluated at baseline, 1 month and 6 months post third dose of booster vaccine. Adverse events related to third dose of vaccination will be surveyed in the 14 day period following third dose of vaccine, and again 1 month following third dose. The study protocol may be altered if booster doses become available that are intended to target new SARS-CoV-2 variants. Furthermore, the study design will be adaptive, as if patients do not respond to a third dose of vaccine the study protocol may be amended to consider other vaccine booster interventions. All study practices will follow social distancing measures currently recommended by Public Health authorities.

5 PARTICIPANT SELECTION and WITHDRAWAL

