10.5.2 Statistical Analysis of Secondary Outcomes

Secondary outcomes will include the proportion of patients who attain Anti-Spike median convalescent serum at 1 month (30 days) following third dose of vaccine. Differences in relative antibody levels (Anti-Spike and Anti-RBD) and neutralizing antibodies between study groups will be assessed through the Mann-Whitney test. The relative levels of antibodies will be tracked

longitudinally for each patient permitting analysis of SARS-CoV-2 antibody kinetics following vaccination and will be assessed through a mixed-effects repeated measures model with random intercepts and fixed covariates following log transformation of relative ratios, which will be exploratory. Differences in serial levels in relative antibody levels will be compared through a mixed effects model as above. Similar to the primary outcome, those with a new positive Anti-NP serologic test or COVID-19 nasopharyngeal swab during the study will be excluded from analysis. An intention to treat analysis will be followed, although an exploratory per protocol analysis may also be reported.

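### If patients' log antibody levels decline at different rates, the random-intercept model in section 10.5.2 understates the standard error of between-booster durability contrasts

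*Combined protocol and SAP*

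**What the plan says.** Section 10.5.2 analyses antibody kinetics with a "mixed-effects repeated measures model with random intercepts and fixed covariates following log transformation of relative ratios". The sentence goes on to give the model's status: "following log transformation of relative ratios, which will be exploratory". The next sentence extends its use: "Differences in serial levels in relative antibody levels will be compared through a mixed effects model as above". The Protocol Summary says, without the exploratory label, "Mixed effects models will be used for comparison of longitudinal antibody levels".

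Section 4.1 sets the schedule: "SARS-CoV-2 antibodies will be measured 1 month, 3 months, 6 months and 12 months post booster vaccination". Antibody levels at 3, 6 and 12 months are secondary outcome 2 in the Protocol Summary and in section 3.2.

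On how patients behave over time, the Figure 1 legend in section 2.2 says "Patients have been divided into 5 clusters by k-clustering based on trajectory of anti-RBD response over time". Cluster 1 maintains its response. Cluster 2 "had an Anti-RBD response but gradually exhibits declining titers". In cluster 3, "some of the participants had more rapid decline in antibody levels". Cluster 4 generally never seroconverts.

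**The concern.** Read literally, a random intercept with independent residuals makes every patient's log-antibody curve parallel apart from noise. It forces the same variance at every visit and the same correlation between any two visits. If patients decline at different rates, two visits far apart differ by more than that model allows, so uncertainty about change over a long interval is understated.

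The contrasts affected are those that ask whether one booster's response lasts longer than the other's. Section 13.3.1 says the results may inform provincial or national policy, including whether one vaccine is better for boosting. A difference in durability reported with an interval that is too short would bear on that question.

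**Working it through.** **Inputs from the documents.** Follow-up visits at 1, 3, 6 and 12 months (section 4.1); random intercepts on the log scale (section 10.5.2); 1:1 allocation within prior-vaccine stratum; target 300 with up to 10% loss (section 10.2). With equal strata, which is an assumption, that leaves 300 × 0.9 / 4 = 67.5, or about 67 per group. The documents give no figure for the longitudinal model, so there is none to reproduce.

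**Assumptions not in the documents.** Patient i at month t has log level aᵢ + bᵢt + noise. The residual SD is σ = 0.3, the between-patient SD is 0.8, and the slope SD is s per month. SDs of the 11-month decline of 0.22, 0.44, 0.66 and 0.88 correspond to s = 0.02, 0.04, 0.06 and 0.08 (divide by 11). Data are complete.

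**Step 1: what the random-intercept fit estimates.** The mean visit time is 5.5. The squared deviations sum to 20.25 + 6.25 + 0.25 + 42.25 = 69, and 69/3 = 23. In large samples the fitted residual variance is therefore σ² + 23s².

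**Step 2: month 12 minus month 1, per patient.**
- Variance used by the model: 2σ² + 46s².
- True variance: 2σ² + 11²s² = 2σ² + 121s².

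The intercept cancels, so neither the between-patient SD nor the intercept-slope correlation enters. The sample size cancels from the ratio, so more patients do not help. Because 46 < 121, the model standard error is too small whenever s > 0.

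**Step 3: numbers (2σ² = 0.18).** Type I error is P(|Z| > 1.96 × ratio).

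| SD of 11-month decline | Model variance | True variance | SE ratio | Type I error |
|---|---|---|---|---|
| 0.22 | 0.1984 | 0.2284 | 0.93 | 6.8% |
| 0.44 | 0.2536 | 0.3736 | 0.82 | 10.6% |
| 0.66 | 0.3456 | 0.6156 | 0.75 | 14.2% |
| 0.88 | 0.4744 | 0.9544 | 0.71 | 16.7% |

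For s = 0.05, 0.10 and 0.15 the ratios are 0.78, 0.68 and 0.65, and nominal 95% intervals cover about 87%, 82% and 80%. The floor is √(46/121) = 0.62, or about 77% coverage. Simulation with 67 per arm (4,000 runs) agrees: about 87% for s = 0.05, 80% to 82% for s = 0.10 and 80% for s = 0.15. With no slope variation, coverage was 95.4%.

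If time were instead fitted as linear, the variance ratio would be (σ² + 23s²)/(σ² + 69s²). Type I error for booster by time would then be 7.2%, 11.9%, 16.1% and 19.0%. Section 10.5.2 specifies no linear term, so the table above is the fairer measure.

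**Step 4: single visits.** Here the model uses the average of the four visit variances. Taking the starting level at month 1 and u = t − 1, the true variance is 0.64 + 2ρ(0.8)su + s²u² + 0.09, where ρ is the correlation of starting level and slope.

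For s = 0.02 and ρ = −0.5 the four variances are 0.7300, 0.6996, 0.6600 and 0.6024, with mean 0.6730. The SE ratio is √(0.6730/0.7300) = 0.96 at month 1 (too narrow) and √(0.6730/0.6024) = 1.06 at month 12 (too wide). Type I error in all scenarios:

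| SD of 11-month decline | ρ = 0: month 1 | ρ = 0: month 12 | ρ = −0.5: month 1 | ρ = −0.5: month 12 |
|---|---|---|---|---|
| 0.22 | 4.8% | 5.5% | 6.0% | 3.8% |
| 0.44 | 4.1% | 7.0% | 6.5% | 3.7% |
| 0.66 | 3.3% | 9.1% | 6.5% | 4.8% |
| 0.88 | 2.4% | 11.6% | 5.8% | 7.0% |

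The direction at a single visit therefore depends on a correlation that the documents do not give.

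**Step 5: the remedy.** With an unstructured covariance, simulated coverage was 94.4% to 95.2% for the month 1, month 12 and month 12 minus month 1 contrasts. That held in four scenarios: intercept SD 1, s = 0.05 or 0.10, correlation 0 or −0.6.

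**The case against.** **The model is exploratory.** This is correct, and no confirmatory claim rests on it. The label limits what may be concluded from a p-value. It does not make an interval with roughly 80% to 87% coverage acceptable as a 95% interval, and this is the only model named for serial levels.

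**Other tests cover single visits.** Section 10.5.2 sends between-group differences in antibody level to the Mann-Whitney test, and section 10.5.1 uses chi-squared or Fisher's exact tests for the primary outcome. Neither depends on this covariance. This stands, and it confines the point to contrasts of change over time.

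**The pilot does not refute the model.** Figure 1 covers 13 weeks after dose two of BNT162b2 in hemodialysis patients, not 12 months after a booster, and its levels are ratios. Declines that differ on the ratio scale can be parallel on the log scale, and differences in level between clusters are absorbed by the intercept. This also stands: the pilot makes varying slopes plausible but does not measure them.

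**The assumed SDs may be too large.** The largest decline SD (0.88) exceeds the assumed between-patient SD (0.8). At the mildest value the error is 6.8%, which is modest.

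**The plan is not final.** Section 10.5 leaves the final analysis plan to be developed, and section 10.5.2 does not say that random intercepts are the only covariance term. That is a reason to settle the wording now, since as written it points to a parallel-curves model.

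**A stronger reading.** A reader might infer that error bars are necessarily too narrow at month 12 and too wide at month 1. That needs variance to grow with time. The pilot does not settle this: cluster 4 starts low with little to lose, while cluster 1 is high and maintained. With ρ = −0.5, month 1 is too narrow in all four scenarios and month 12 too wide in three.

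**Conclusion.** The point holds for durability contrasts. If log-scale slopes vary between patients and no further covariance term or robust standard error is added, the standard error for booster by time, or for month 12 minus month 1, is too small. This does not depend on the intercept-slope correlation or the sample size. The size, 6.8% to 16.7% against a nominal 5%, rests on assumed SDs and on decline that is linear in time on the log scale. With no slope variation there is no error.

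No direction can be stated for single-visit standard errors, and the documents do not show that the pilot disproves the model. This is worth correcting before the analysis plan is finalised, but it does not threaten the primary result.

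**What to change.** In section 10.5.2, replace the random-intercept specification with:
- log antibody level at each visit, with visit as a categorical factor;
- booster-by-visit fixed effects within prior-vaccine stratum;
- an unstructured within-patient covariance with Kenward-Roger degrees of freedom;
- if that does not converge, a random intercept plus random slope with robust (sandwich) standard errors.

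Keep the exploratory label if that is the intention, and use it consistently in the Protocol Summary.

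The cost is a change of wording, with no new data or visits. Intervals for durability contrasts will be somewhat wider. There are more covariance parameters to estimate: 4 × 5 / 2 = 10 for the four follow-up visits, or 5 × 6 / 2 = 15 if baseline is modelled as an outcome, against 2 for a random intercept and residual.

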5.5.2 Blinding and Unblinding

Trial participants, study investigators, research team member, outcome assessors, and data analysts will be blinded to the intervention randomization. The individual dispensing and administering the vaccine will be aware of the vaccine being dispensed and administered but the patient will be blinded. Patients will be un-blinded to the vaccine they received following completing of adverse events following immunization reporting (30 days) and at that point will be provided with a vaccine receipt.

Un-blinding will only occur under exceptional circumstances where knowledge of the vaccine received is essential for further management of the study participant. Physicians are encouraged to discuss with the Qualified Investigator if un-blinding is necessary. If un-blinding is considered necessary, the Qualified Investigator will contact the randomization centre, who will do the code break as deemed necessary and communicate it directly to the attending physician. The Qualified Investigator will report all code breaks as they occur on the case report form.

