The third dose of vaccine will be administered between 2 months to 12 months following second dose of vaccine to allow a reasonable window for eligibility, and to allow for the appropriate screening of study participants with suboptimal initial humoral serologic response for this study. Vaccine will be dispensed by the central pharmacies through concealed allocation prior to planned administration of the study intervention. The vaccine will be administered by an individual who

has been trained in COVID-19 vaccine administration. The individual administering the vaccine will not be blinded to the vaccine type. Vaccine receipt will be entered in the COVAX database, and receipt of a booster vaccine dose will be recorded in the Ontario Renal Network COVID-19 vaccine tracker after unblinding following reporting of the adverse events at 30 days.

Participants will be provided with documentation indicating that they have received a third booster dose and the date that this was received after unblinding following the completion of adverse event following immunization. As with standard vaccine administration, participants will sign additional informed consent to receive the vaccine and confirm that they do not have allergies to the components of either vaccine type. Participants will be monitored for 15 minutes following vaccine administration prior to being allowed to return home. For in-centre hemodialysis participants, the vaccine administration will occur during maintenance hemodialysis.

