6.1.7 Prior and Concomitant Medications/Treatments

Information regarding receipt of COVID-19 vaccination will be documented to determine study eligibility with stratification determined by receipt of *BNT162b2* and *mRNA-1273*. In addition, a booster dose of vaccine will not be administered within 14 days of another vaccine (e.g. Hepatitis B or Shingle vaccination).

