The ICF will be signed and dated by the participant and individual obtaining consent. The consent process will be documented in the clinical or research record. The original ICF, in its entirety, will be maintained by the site, and a complete copy of the signed ICF provided to the participant. The rights and welfare of the participants will be protected by emphasizing to them that the quality of their clinical care will not be adversely affected if they decline to participate in this study. The provision of consent is an ongoing process

and should be maintained throughout the duration of the study. Participants may withdraw consent at any time throughout the course of the study. Patients may request access to their study results from their primary nephrologist or the study coordinator. Results will not appear on their electronic medical record. Risks and benefits to participations in the study are outlined below.

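### COVID-19 vaccine doses received after the study booster have no follow-up field and no analysis rule, so the 3-, 6- and 12-month antibody comparisons could credit their effect to the third dose.

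*Combined protocol and SAP*

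**What the plan says.** Secondary objective 2 (Section 3.2) concerns the humoral response at 3, 6 and 12 months. Section 4.1 gives the schedule: "SARS-CoV-2 antibodies will be measured 1 month, 3 months, 6 months and 12 months post booster vaccination". Section 10.5.2 analyses the repeated levels on the log scale with a random-intercept mixed model, labelled exploratory, and adds: "Differences in serial levels in relative antibody levels will be compared through a mixed effects model as above". It also plans Mann-Whitney comparisons of antibody levels between groups, without naming a time point or calling them exploratory. The secondary analyses follow intention to treat, with an optional per-protocol analysis whose population is not defined.

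New infection is the one post-booster event with a rule: Sections 7.2.3 and 10.5.2 exclude participants who become infected.

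On vaccination history, Section 6.1.7 says: "Information regarding receipt of COVID-19 vaccination will be documented to determine study eligibility with stratification determined by receipt of" the two products. Section 10.5 reports the timing of doses one to three. Section 7.3 sends vaccine type and vaccination dates to the laboratory with the samples. Section 6.1.3 enters the study dose in COVAX and adds that "receipt of a booster vaccine dose will be recorded in the Ontario Renal Network COVID-19 vaccine tracker". Section 8.7 describes that tracker, and PROMIS in British Columbia, as systems for following vaccine-related adverse events.

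Participants learn their product once the 30-day adverse event reporting is complete (Section 5.5.2). Section 13.3 states: "Patients may request access to their study results from their primary nephrologist or the study coordinator".

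**The concern.** Section 7.2.3 sets out to keep infection from contaminating the antibody results. A further vaccine dose contaminates the same measurements. It raises anti-RBD and anti-Spike, but Section 7.2.1 notes that the nucleocapsid antigen is not targeted by the vaccines available in Canada, so Anti-NP stays negative and the infection exclusion does not remove the sample. Unless the dose is recorded, the sample enters the model as a third-dose value.

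At stake is the meaning of the durability results. Further doses at the same rate in both arms would make the third dose look longer-lasting than it is. Doses at different rates could create, shrink or reverse a difference between the two boosters. Knowledge of the product from day 30, and access to results on request, make uptake that depends on arm or titre possible.

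**Working it through.** **1. Is a later dose captured?**

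- *Table 1 and Appendix A.* The 3-, 6- and 12-month rows hold antibody sampling, plus PBMC at 6 months. There is no vaccination question.
- *Section 6.1.7.* Its stated purpose is eligibility and stratification, which concern the first two doses. Its 14-day spacing rule concerns giving the study booster.
- *Section 7.4.* The variables are baseline variables.
- *Section 10.5.* Timing is reported for doses one to three only.
- *Section 7.3.* Vaccination dates travel with the samples, and no visit is exempted. The text does not say whether doses after the study booster are included.
- *Sections 6.1.3 and 8.7.* COVAX, the Ontario Renal Network tracker and PROMIS may hold later doses. Neither section says that they will be extracted for the trial.

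Later doses may thus be on file somewhere, but no section says that the study captures or uses them.

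**2. Is a later dose handled?** Section 10.5.2 has no covariate, censoring point or sensitivity analysis for one, and does not say whether the target is the effect of the assigned booster whatever follows or the durability of the third dose alone.

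**3. Which results are exposed?** The 1-month sample coincides with unblinding, give or take the 7-day window in Section 8.9.1, so the primary outcome has almost no exposure. The exposed results are the 3-, 6- and 12-month levels.

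**4. How large could the distortion be?** The plan states no figure for later doses. The inputs are:

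- *Fold rise F from a further dose.* The only guide is the French hemodialysis study in Section 2.3: a median increase above 580% after a third dose, so F = 1 + 5.8 = 6.8. Carrying this over to a later dose is an assumption, and it ignores waning before the sample. F = 3 is taken as a lower assumption.
- *Uptake by arm, u_A and u_B.* Not in the documents. Differences d = u_A − u_B of 0.10, 0.20 and 0.30 are assumed.

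If each further dose multiplies titre by F, the mean log titre of an arm moves by u × log F. With no true difference between arms, the spurious geometric mean ratio is exp(d × log F) = F^d.

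| d | F = 3 | F = 6.8 |
|---|---|---|
| 0.10 | 3^0.10 = 1.12 | 6.8^0.10 = 1.21 |
| 0.20 | 3^0.20 = 1.25 | 6.8^0.20 = 1.47 |
| 0.30 | 3^0.30 = 1.39 | 6.8^0.30 = 1.78 |

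With equal uptake u, this model leaves the ratio between arms unchanged but multiplies the level in both arms by F^u. At u = 0.20 that is 1.25-fold (F = 3) to 1.47-fold (F = 6.8), which overstates persistence after the third dose.

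**The case against.** The strongest reply has four parts.

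*The data may already exist.* Section 7.3 attaches vaccination dates to sample lists, and provincial systems may hold later doses. This stands in part. It rules out saying that vaccination is documented solely at entry, and it makes the remedy cheap. It does not supply a study field or a rule for use.

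*The analysis is exploratory and the primary outcome is safe.* Both are correct and limit the weight of the point. The objective is still listed as secondary, and the Mann-Whitney comparisons are not called exploratory.

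*Intention to treat is a legitimate choice.* It is: including every sample whatever happened later is a valid treatment-policy comparison, so it should not be displaced. But Section 10.5.2 also describes the aim as antibody kinetics after vaccination, which is a different question, and an all-samples result is hard to interpret if the number of later doses is unknown.

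*Nothing shows that later non-study doses will occur.* A reader might infer that the protocol itself expects them. The documents do not support this. Sections 4.1, 5.5 and 7.1 discuss approval of a booster only as a reason to relax serologic entry criteria, which concerns the third dose. The other passage in Section 4.1, "if patients do not respond to a third dose of vaccine the study protocol may be amended to consider other vaccine booster interventions", describes a possible amendment, which could carry its own rules. A reader might likewise infer that low responders, or the arm seen as weaker, would seek more doses. No passage says so; under Section 13.3 results are given on request and stay off the electronic medical record. Both are plausible inferences and no more.

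**Conclusion.** The point holds as a gap in data capture and analysis for the later secondary comparisons. The plan has no explicit follow-up field for further COVID-19 vaccine doses and no rule for samples taken after one, and the planned serology cannot identify them.

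Its size is conditional. For uptake differing by 10 to 30 percentage points and a further dose worth 3- to 6.8-fold, the spurious geometric mean ratio runs from 1.12 to 1.78. If uptake is nil there is no distortion; if it is equal, the ratio between arms is undisturbed under the constant-multiplier model and only the apparent durability is inflated. Uptake, its dependence on arm, and the fold rise are all assumptions.

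The documents do not support reading this as a threat to the primary outcome, as evidence that bias will occur, or as an error in choosing intention to treat.

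**What to change.** 1. In Table 1 and Appendix A, add at 3, 6 and 12 months the date and product of any COVID-19 vaccine received since the study booster. Check the answers against COVAX, the Ontario Renal Network tracker or PROMIS. Section 8.7 describes the tracker as covering chronic dialysis patients, so non-dialysis participants depend on the question and the other registries.
2. In Section 10.5.2, keep the intention-to-treat analysis of all samples and state that it is a treatment-policy comparison.
3. Add a pre-specified durability analysis: the same mixed model, with antibody values censored from the date of the first further dose and all earlier samples kept.
4. Report the number and timing of further doses by group.

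Section 10.5 leaves the final analysis plan to be developed, so items 2 to 4 can go there.

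The cost is one CRF item at visits already held and fewer late samples in the durability analysis. That analysis relies on values being missing at random given earlier titres. Random intercepts alone may satisfy this only in part: if rates of decline vary and faster decliners are re-dosed sooner, censoring could itself overstate durability. This is a further reason to report both analyses side by side.
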